Adverse events will be reported in accordance with the guidelines of the Institutional Review Board (IRB) and the Food and Drug Administration (FDA). Concomitant medications will be recorded. All serious adverse events, regardless of causation, will be reported to the IRB and Amgen Global Safety (see below) within one working day. All serious and medically significant adverse events considered related to etanercept by the investigator will be followed until resolved or considered stable. Unexpected and fatal or life-threatening events will be reported to the FDA by phone or FAX within 7 calendar days. Written reports will be sent to the FDA within 15 calendar days for any serious unexpected adverse events for which there is reasonable possibility that the event may have been caused by the study drug. Any pregnancies occurring on study must also be reported to Amgen Global Safety (see below). Within 24 hours of FDA notification, a copy of all FDA submitted reports will be sent to Amgen by facsimile or mail at the following address:

Amgen Global Safety  
c/o Amgen  
[name]  
[name]  
*[name]*  
*[contact]*

At the screening visit, subjects will have a TB test performed, as well as skin exams, physical exams, medical history review, etc. as documented in the study flow sheet to determine if they meet the entrance requirements.

Peripheral blood and biopsies will be obtained from 50 psoriatic patients with active lesions, who have not received any systemic treatment for four weeks, or any topical treatment other than bland emollients for two weeks. Peripheral blood mononuclear cells (PBMC) will be isolated from blood (approximately 4-6 tubes) taken from psoriatic patients prior to treatment and at every visit of etanercept treatment (see flow chart). The isolated PBMCs will be cryopreserved and stored in liquid nitrogen, or used immediately for experiments. Serum will be stored for future cytokine measurements and levels of anti-nuclear antibodies (ANA) by ELISAs. Cellular staining will be determined by twelve-color BD LSR II flow-cytometer. Two biopsies will be taken at baseline (uninvolved and lesional psoriatic skin) and at each visit (lesional only) at week 2, 6 and 12. Gene and protein expression may be analyzed in whole-biopsies, or certain cell populations may be isolated from biopsies to perform flow cytometry, gene expression studies, protein expression studies, and other laboratory studies.

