1. Demonstrate that the strength of type I IFN signature in psoriatic skin predicts treatment response.

Fifty individuals with moderate to severe psoriasis with high dose etanercept (50mg twice weekly), and the composition of the lesional psoriatic cytokine network will be tracked at the onset (day 0), early (week 2), during the middle (week 6) and at the end of treatment (week 12). Serum samples and PBMC isolation will be done at each time-point for later analyses. Biopsies of uninvolved and lesional skin will be performed before initiation of treatment and then lesional biopsies taken at week 2, week 6 and week 12. Skin will be anaesthetized with 1% lidocaine with epinephrine and 6mm punch biopsies will be taken. Photographs of patients will be obtained and the anatomical location of biopsies recorded. Biopsies will be bisected, with one-half snap frozen in liquid nitrogen and stored at -80° until RNA and protein processing and the other half fixed in 4% formalin for paraffin embedding and immunohistochemistry. Processing will be performed as previously described by our team and only high quality RNA, as determined by Agilent 2100 Bioanalyzer will be used .

Next-generation sequencing of RNA (RNAseq) will be performed on the samples according to Illumina's protocol using 2 $\mu$ g of RNA. Immunohistochemistry will be performed to validate findings with MXA staining used to confirm presence of type I interferon signal. H&E staining will be used to assess the degree of epidermal hyperplasia and response to treatment and immunohistochemical detection of keratin 16, CD3, CD11c, CD163, Ki67 used to validate the degree of histologic response in context of the clinical response. QRT-PCR will be performed for selected gene transcripts to validate the findings of RNAseq.

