**Analysis/Statistics:** RNAseq reads will be mapped using the TopHat algorithm and gene expression levels will be expressed as reads per kilobase of region per million mapped reads (RPKM). Based on prior experience, we estimate that we will obtain around 3 gigabases of sequence for each sample. Inflammation profiles and cytokine signature scores will be calculated as described by our group. Estimating that around 50% of patients will achieve a 75% reduction in Psoriasis Area and Severity Index (PASI) (PASI75) at 12 weeks; this should allow us to determine if effective treatment is associated with complete neutralization of the TNF signal in lesional psoriatic skin and elucidate the effect of the strength of the type I IFN signal on treatment response. For our statistical analyses, we are interested in one outcome variable (PASI score) and two continuous covariates (RNAseq-generated TNF- $\alpha$  signal and IFN- $\alpha$  signal). We anticipate that these data will be analyzed in two ways.

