(1) First, we will test whether temporal change in PASI score is significantly associated with baseline TNF- $\alpha$  signal, baseline IFN- $\alpha$  signal, and/or an interaction between these two baseline signals. Along these lines, a cumulative score reflecting change in PASI during the course of etanercept treatment will be calculated for each patient. This score will then be treated as a continuous response variable, and we will use robust linear modeling to test whether scores are significantly associated with baseline TNF- $\alpha$  signal, baseline IFN- $\alpha$  signal, and/or an interaction between these two signals. In addition, we expect that it will be possible to unambiguously classify 30% of patients as non-responders, with an equal percentage showing clear improvement in PASI score, and the remainder showing an intermediate response. Accordingly, we will also categorize patients according to improvement in PASI score (i.e., responders, intermediate-responders, and non-responders), and use cross-validation to calculate AUC statistics to directly quantify the capacity of baseline TNF- $\alpha$  and IFN- $\alpha$  signals to predict patient response status. Based upon preliminary data ( $n$  = 15 patients), we anticipate that improved PASI score will be associated with a heightened baseline TNF- $\alpha$  signal and weakened baseline IFN- $\alpha$  signal. The proposed study design will allow us to not only confirm this expectation, but will provide increased power to assess a possible TNF- $\alpha$ /IFN- $\alpha$  interaction effect, and to better characterize quantitative thresholds associated with response and non-response.

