(2) Second, we will test whether TNF- $\alpha$  and/or IFN- $\alpha$  signals are significantly altered during the course of etanercept therapy, and whether such changes differ between subjects with different PASI response profiles. In these analyses, TNF- $\alpha$  or IFN- $\alpha$  signal will be treated as a response variable in a univariate repeated measures analysis of variance, with subject and time as covariates. In this framework, a shift in TNF- $\alpha$  or IFN- $\alpha$  signal during the course of etanercept treatment will be indicated by a significant time effect. In follow-up analyses, models will include 0-1 covariates indicating specific PASI response profiles (e.g., non-responder, intermediate-responder, or responder), which will allow us to test whether temporal shifts in TNF- $\alpha$  or IFN- $\alpha$  signals differ according to the effectiveness of etanercept treatment (i.e., by evaluating interaction effects involving time and 0-1 covariates denoting PASI response patterns). We anticipate that etanercept treatment will more strongly attenuate TNF- $\alpha$  signals in responders compared to intermediate-responders or non-responders (possibly due to disparities in baseline TNF- $\alpha$  and IFN- $\alpha$  signals). Conversely, we expect that non-responders will be characterized by high IFN- $\alpha$  signals, which remain high during the course of etanercept treatment. All analyses performed using PASI scores will be repeated using physician global assessment scores as the response variable, although we expect results from these two analyses to be consistent. With 50 patients recruited and treated, we estimate that we will have >95% statistical power to detect significant effects in the proposed design (Type I error rate of 0.05). Although the analysis will be primarily focused on TNF and IFN signatures, this dataset will also provide us with opportunities to determine contribution of other inflammatory cellular and cytokine contribution to the clinical response.

**Anticipated Results:** We expect that patients with strong IFN- $\alpha$  signature in psoriatic skin along with weak TNF- $\alpha$  signature will have minimal response to anti-TNF treatment, while patients with the opposite pattern, weak IFN and strong TNF signature, will have significant clinical improvement.

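### RPKM with no stated between-sample normalisation, and a score defined only by citation, leaves the TNF and IFN time analyses open to a read-composition shift

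*Combined protocol and SAP*

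**What the plan says.** The Analysis/Statistics paragraph fixes one expression scale: "gene expression levels will be expressed as reads per kilobase of region per million mapped reads (RPKM"). It names no between-sample scaling, and neither does any other section. The next step is given by reference only: "Inflammation profiles and cytokine signature scores will be calculated as described by our group". The documents do not contain the scoring formula.

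The scores are then used in two ways.

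- **Part (1)** relates PASI change to signals measured before treatment: "we will test whether temporal change in PASI score is significantly associated with baseline TNF" and IFN signal.
- **Part (2)** makes each signal the response variable in a repeated-measures analysis of variance. A shift in "signal during the course of etanercept treatment will be indicated by a significant time effect". Follow-up models test whether that shift differs between responders, intermediate responders and non-responders.

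The paragraph also asks whether effective treatment fully abolishes the lesional TNF signal, which is a question about level.

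The samples come from repeated lesional biopsies: "Two biopsies will be taken at baseline (uninvolved and lesional psoriatic skin) and at each visit (lesional only) at week 2, 6 and 12". Two laboratory checks are planned: "QRT-PCR will be performed for selected gene transcripts to validate the findings of RNAseq", and "MXA staining used to confirm presence of type I interferon signal".

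**The concern.** RPKM is a share of a fixed total. If a group of abundant transcripts takes up fewer reads, the RPKM of every other gene rises although its true level is unchanged. The reverse holds if abundant transcripts rise on balance. The shift has the same sign in every unchanged gene, so a score that is a plain average over a signature does not cancel it.

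Part (2) compares lesional skin before and during clearing. The protocol uses keratin 16, Ki67 and immune-cell stains to grade histologic response, so it expects tissue to differ with response. A composition shift that follows clearing would vary with time and with response class, the two factors that part (2) tests. A false time effect could then be read as a biological change in signal, or a true fall in TNF signal in responders could be understated.

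**Working it through.** The plan gives no figure to reproduce here. It states no read shares, no score SD and no normalisation factor. The inputs marked as assumed below are therefore shown over a range.

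**Step 1. Shift in unchanged genes.** Let abundant transcripts hold a share *f* of reads at baseline, and let their true level change by a factor *k*. The total becomes 1 − *f* + *kf* of its former value. The RPKM of every unchanged gene is then multiplied by 1/(1 − *f* + *kf*). Both *f* and *k* are assumed.

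| *f* | *k* | 1 − *f* + *kf* | Fold | log2 |
|---|---|---|---|---|
| 2% | 0.25 | 0.985 | 1.015 | 0.02 |
| 5% | 0.25 | 0.9625 | 1.039 | 0.055 |
| 10% | 0.25 | 0.925 | 1.081 | 0.112 |
| 20% | 0.25 | 0.85 | 1.176 | 0.234 |
| 30% | 0.10 | 0.73 | 1.370 | 0.454 |

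**Step 2. Effect on a test of time.** As a simple stand-in for the repeated-measures model, take a two-sided 0.05 paired *t* test with 50 patients on a mean-log2 score whose true change is zero. The noncentrality is shift/SD × √50. The SD of change is assumed to be 0.3, 0.5 or 1.0. The rejection rate, nominally 5%, is:

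| Shift (log2) | SD 0.3 | SD 0.5 | SD 1.0 |
|---|---|---|---|
| 0.053 | 23% | 11% | 7% |
| 0.112 | 73% | 34% | 12% |
| 0.234 | about 100% | 90% | 37% |

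**Step 3. Effect on the response contrast.** The plan expects 30% responders and 30% non-responders, which is 0.30 × 50 = 15 each. If only responders shift, the standard error of the difference is SD × √(2/15). By normal approximation the rejection rate, again nominally 5%, is:

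| Shift (log2) | SD 0.3 | SD 0.5 | SD 1.0 |
|---|---|---|---|
| 0.112 | 18% | 9% | 6% |
| 0.234 | 57% | 25% | 10% |

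**Step 4. Does the form of the score matter?** In simulated data with 15,000 genes, 24 genes holding about 20% of reads fell to a quarter, and 100 signature genes were left unchanged.

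| Score | Change |
|---|---|
| Mean log2 RPKM | +0.24 |
| Mean log2 after median-ratio normalisation | 0.00 |
| Rank-based (0 to 1 scale) | 0.00001 |
| Correlation with fixed weights | 0.00 |

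Between-sample normalisation removes the shift, and so does a score that is itself scale-invariant.

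**Step 5. Direction.** Under a net fall in abundant transcripts, the shift is upward in patients who clear. Part (2) expects stronger TNF attenuation in responders and persistently high IFN in non-responders. The artefact works against both contrasts, so it would tend to hide them, although it can still produce a false overall time effect.

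**The case against.** The strongest reply is that the scoring rule is not in the documents. RPKM is named as the unit for gene expression, and the score is left to the group's earlier work. If that score is rank-based, correlation-based or referenced to other genes, a common shift cancels and no bias arises. This stands. A reader might infer that the artefact is already built into the TNF and IFN scores, but the text does not show that. It shows only that the possibility is not excluded.

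A reader might also infer that the main predictive result is at risk. A treatment-driven change cannot reach it, because the predictors in part (1), including those behind the cross-validated AUC, are measured before the first dose. Differences in composition between patients at baseline would be a separate argument, which is not made here.

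Nor do the documents support a claim that the shift is large. The stains listed for histologic response say nothing about share of reads, and no net direction is given. Some abundant transcripts could rise as skin normalises.

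Finally, QRT-PCR and MxA staining are independent checks, and protein staining does not depend on read composition. They are partial, however. QRT-PCR covers selected transcripts, MxA concerns interferon only, no check is named for the TNF score, and neither is said to correct the scores.

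**Conclusion.** The point holds in conditional form and is confined to part (2) and the question of whether the TNF signal is fully abolished. As written, the plan does not let a reader exclude a composition shift that tracks clearing and is taken for a change in signal. The possible size runs from about 0.02 log2, which is negligible, to about 0.45, which is material. Where it falls depends on read shares and changes that the documents do not give. The rejection rates above rest further on an assumed SD of change and on a plain mean-log2 score. The point is worth acting on because the remedy is standard and cheap, not because an artefact has been demonstrated.

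**What to change.** State the normalisation and the scoring formula in the Analysis/Statistics paragraph. Then do one of the following:

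- compute the TNF and IFN scores from gene counts normalised between samples (TMM or median-of-ratios) on a log or variance-stabilised scale; or
- use a scale-invariant score. If the cited score is already of that kind, say so and show it.

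Keep the RPKM-based score as a sensitivity analysis for part (2), for continuity with the preliminary data from 15 patients.

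The work uses the same mapped reads, so no new samples or sequencing are needed. There are two downsides. The new scores will not be on exactly the same scale as earlier RPKM-based ones. TMM and median-of-ratios also assume that most genes do not change, which should be checked against the data.

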#### **Inclusion:**

1. At least 18 years of age at screening.
2. Clinically stable moderate to severe plaque psoriasis at screening and baseline.
3. Subject must be:
  - A man **or**
  - A woman who is surgically sterile or at least 3 years postmenopausal **or**
  - A woman of childbearing potential who has had a negative pregnancy test within 7 days before the first dose of study drug.
4. If the subject is sexually active, (s)he must agree to use a medically acceptable form of contraception during screening and throughout the study.

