17. Latex sensitivity [Nota Bene: only applicable if they are using prefilled syringe or prefilled SureClick™ autoinjector presentations]
18. Exposure to hepatitis B or hepatitis C or to high risk factors for hepatitis B or C, such as intravenous drug use in patient.
19. Systemic lupus erythematosus, history of multiple sclerosis, transverse myelitis, optic neuritis or seizure disorder.
20. Use of a live vaccine 90 days prior to screening visit, or concurrent use of a live vaccine.
21. Any condition or circumstances judged by the patient's physician[or the investigator or medically qualified study staff] to render this clinical trial detrimental or otherwise unsuitable for the patient's participation.
22. History of non-compliance with other therapies.
23. Pregnant or nursing females.

24. Diagnosis of multiple sclerosis in first degree family relationship (parent, sibling or child)

Flow Chart of visits:

Visits	Screening	BL	Week2	Week 6	Week 12
ICF	X				
Med/Hx	X				
Con Meds	X	X	X	X	X
Biopsies		X	X	X	X
Inc/exc	X				
Screening labs (CBC, metabolic panel)	X				
TB Test*	X				
Blood		X	X	X	X
Dispense Drug		X	X	X	
Urine Pregnancy Test	X	X		X	
Photos		X	X	X	X
Injection Instruction		X			
Physical Exam	X	X			
PASI/PGA/BSA/ Itch Assessment**	X	X	X	X	X

\*Subjects will be tested for TB at the screening visit and will return to research clinic 2 days later so that the area can be examined and the result documented.

\*\*Subjects will be asked to verbally indicate their level of itch on a scale of 0 to 10 at each visit.

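### Analysis (1) gives no scale for the PASI-change score and omits baseline PASI; if the score is in points, spread in baseline PASI lowers power for the IFN test

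*Combined protocol and SAP*

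**What the plan says.** Aim 1 is to show that the "strength of type I IFN signature in psoriatic skin predicts treatment response". The Analysis/Statistics section tests this in its item (1). The outcome is described as "a cumulative score reflecting change in PASI during the course of etanercept treatment will be calculated for each patient", with no formula and no unit. For the model, "we will use robust linear modeling to test whether scores are significantly associated with baseline" TNF signal, baseline IFN signal and their interaction. Item (1) also sorts patients into three response classes and expects that "it will be possible to unambiguously classify 30% of patients as non-responders".

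The same section assumes that "around 50% of patients will achieve a 75% reduction in Psoriasis Area and Severity Index". That is a relative measure, but it is used there to state an expected response rate, not to define the score. The two cytokine signals are named as the covariates of interest. Baseline PASI is neither listed nor ruled out.

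The visit flow chart schedules "PASI/PGA/BSA/ Itch Assessment" at screening, baseline and weeks 2, 6 and 12, so baseline PASI will be available. Eligibility asks for "Clinically stable moderate to severe plaque psoriasis at screening and baseline" and sets no PASI range. Item (2) adds that "All analyses performed using PASI scores will be repeated using physician global assessment scores as the response variable".

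**The concern.** The wording fits a score in points or in percent. Percent is at least as natural given the reference to PASI75, but nothing commits the analyst to it, and the choice could be made after the data are seen.

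On the points reading, the change a patient can show depends on the starting value. Someone starting at PASI 30 who improves by half drops 15 points; someone starting at 12 who improves by half drops 6. The proportional response is the same, yet the scores differ by a factor of 2.5. With no baseline term, that difference goes into the residual and weakens the IFN test, even when IFN is unrelated to severity.

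If a signal also tracks baseline severity, there is bias as well. The signal can appear to predict change in points without predicting proportional response, or a true IFN effect can be masked. The study has one arm, so randomisation does not protect against this.

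**Working it through.** **The plan's own power figure.** The plan claims more than 95% power with 50 patients at a type I error rate of 0.05, without an effect size, SD or sidedness. It cannot be reproduced, only solved backwards. By Fisher's z, two-sided, r = tanh((1.960 + 1.645)/√47) = tanh(0.526) = 0.48.

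**Why points lose power.** Let points change = B × P, where B is baseline PASI with coefficient of variation CV, and P is proportional improvement with mean m and SD s. If B is independent of P and of IFN,

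r(points) = r(percent) × s / √(s² + CV²(m² + s²)).

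Take r(percent) = 0.482, m = 0.70, s = 0.25, CV = 0.4 (the last three assumed):

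r(points) = 0.482 × 0.25 / √(0.0625 + 0.16 × 0.5525) = 0.1205 / 0.3885 = 0.31.

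Fisher's z power falls from 95% to 59%.

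**Simulation matched to the plan's response rates.**
- From the plan: n = 50; half of patients reach PASI75, so median improvement is 75%; about 30% are non-responders.
- Assumed: log-normal baseline PASI, mean 18, CV 25/40/60%; IFN correlation 0.4 with percent improvement; SD of percent improvement 25/35/48% before a cap at 100%.
- The 30th percentile of improvement is 75 − 0.524 × SD, which gives 62%, 57% and 50%. SD 48% therefore comes closest to the plan's 30% non-responders.
- Model: least squares on TNF, IFN and TNF×IFN, two-sided 0.05, 10,000 trials per scenario.

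IFN power at CV 25/40/60%:

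| SD of percent improvement | Points, no baseline PASI | Points with baseline PASI |
|---|---|---|
| 48% | 63/51/36% | 71/67/62% |
| 35% | 59/43/28% | 73/69/63% |
| 25% | 52/34/21% | 75/71/65% |

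On the percent scale, power is 74–78% without the covariate and 73–77% with it. At SD 48%, unadjusted points fall short of adjusted points by 8, 16 and 26 percentage points (71−63, 67−51, 62−36). They fall short of percent with baseline PASI (73%) by 10, 22 and 37.

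Over the same grid, points without v with baseline PASI give 13–40% v 38–48% at IFN correlation 0.3, and 30–84% v 83–92% at 0.5.

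**Sensitivity of the loss.**
- Huber robust regression, SD 48%: 62/53/43% v 72/71/68%. Robust fitting does not remove the loss.
- Score as an area over weeks 2, 6 and 12 (assumed 30/70/100% of final improvement, with visit noise), SD 48%: 60/48/35% v 68/65/59%.
- No worsening allowed, SD 48%: 62/48/33% v 70/67/61%.

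**If a signal tracks severity (hypothetical correlation 0.3 with log baseline PASI).**
- A TNF signal unrelated to percent improvement is declared significant in 14/21/27% of trials at SD 48%, and in 26/35/39% at SD 25%. With baseline PASI in the model the rate is 5–6%. At correlation 0.1 the unadjusted rate is 6–8%; at 0 it is 5%.
- With no IFN effect, IFN is falsely declared significant in 13–38% v 5%.
- With a true IFN effect of 0.4 (CV 40%, SD 48%), power in the hypothesised direction is 88% at an IFN-severity correlation of −0.3 and 12% at +0.3, v 67% adjusted.

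**What the covariate adds on the percent scale.** If percent improvement itself correlates ±0.3 with baseline PASI, the covariate raises IFN power from 74–78% to 77–81%. It also cuts false TNF rejection, at a TNF-severity correlation of 0.3, from 9–10% to 5%.

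**The case against.** The strongest reply is that the harm sits on a reading the text does not choose. On a percent scale, with percent improvement unrelated to baseline PASI, the missing covariate costs nothing. This stands: the undefined score is the larger defect, and the covariate is mainly insurance once percent is fixed.

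The size is also open to challenge.
- **Baseline spread.** The plan gives no CV. At CV 20% and SD 48% the loss is only about 5 points (67% v 72%), and at CV 10% about 1–2.
- **Response spread.** The largest losses come from SD 25%, where the 30th percentile is still 62% improvement. That is hard to square with a clear-cut non-responder group, so the SD 48% row deserves the most weight.
- **Proportionality.** If improvement scales with the square root of baseline, the loss at CV 40% and SD 48% is about 9 points (59% v 68%). If patients drop a constant number of points, the ranking reverses. In a simulation with r = 0.482 at CV 40%, points give 87%, percent alone 52%, and percent with baseline PASI 81%. However, that model gave PASI75 in only 18% of patients, against the plan's 50%, and it shows why percent should not be adopted without the covariate.
- **Severity link.** No passage supports a correlation of 0.3, so the bias figures are conditional.

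The plan also has a cross-validated AUC for response status, so Aim 1 does not rest on this model alone; but those classes have no cut-offs either. The PGA repeat carries over the same model terms, so it does not settle the question. The benefit of a baseline PGA term was not computed, because the plan gives no PGA scale.

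These points change the size of the loss and show when it disappears. They do not make an undefined scale without a baseline term the better choice.

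**Conclusion.** The concern holds, with moderate confidence, and should be fixed before analysis. It is certain from the text that the score has no stated scale and that no stated model contains baseline PASI. The loss is conditional on a points score and roughly proportional improvement. With an assumed IFN correlation of 0.4 and SD 48%, omitting baseline PASI then costs about 8 to 26 points of IFN power over CV 25–60%, and little if baseline PASI varies by 15% or less. Bias in the TNF and IFN tests arises only if a signal tracks severity, which the documents neither support nor exclude. With percent change unrelated to baseline PASI, neither problem occurs.

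**What to change.** In item (1) of Analysis/Statistics:
- Define the score in advance as percent change from baseline PASI, in line with the plan's use of PASI75, and give the formula that combines weeks 2, 6 and 12.
- Add baseline PASI as a covariate in the robust linear model, and baseline PGA in the PGA repeat. Read the TNF, IFN and interaction tests from the adjusted model.

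The percent scale removes most of the problem. The covariate covers the case where percent improvement also depends on starting severity, and it is needed if points are kept.

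The cost is two sentences and one degree of freedom, with no new visits, samples or patients. When the covariate is not needed, it takes about 1 point of power on the percent scale (74% to 73% at SD 48%; 78% to 77% at SD 25%).
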